9.3.3 Return to Care for Suicidality (ED utilization)

Return to care for suicidality will be assessed for study participants through self-report at 6 and 12 months and by measuring ED utilization using an electronic health records query to review the number of times each patient returned to SLHS ED, the primary diagnosis, and the reason code (ICD-10). SLHS uses EPIC⁵⁴ electronic health records system, and study staff will work with an informational technology expert trained in EPIC to support data extraction to assist with measuring this outcome. Additionally, study staff may also review available ED dashboards/EDIE System that includes health systems outside of SLHS to measure use of non-SLHS EDs during the study period.

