The C-SSRS is available in a full-length version comprised of 11 yes/no questions plus 7 multiple choice questions and space to collect and record brief narrative explanations. An abbreviated screener version of the C-SSRS consists of 5 yes/no questions related to suicidal ideation and one two-part yes/no question related to suicidal behavior. Both the full-length and screener versions of the C-SSRS are available in a 'lifetime-recent' version (to establish a baseline) and a 'since last contact' version to be administered at follow-up visits. Two versions of the C-SSRS will be used for this study: C-SSRS Lifetime-Recent Screener (given at baseline, in accordance with standard of care at SLHS), and C-SSRS Since Last Contact Screener (given at 6 and 12 months). In addition to using the C-SSRS Screeners at baseline and follow-up, the study will incorporate three items from the full-version of the C-SSRS that are not included in the screener version to measure: (1) Aborted or self-interrupted suicide attempts; (2) interrupted suicide attempts; and (3) actual suicide attempts at baseline, 6, and 12 months. Non-lethal self-harm, lethal means used for attempts or completions, and death by suicide will also be collected. Vital records will be used to measure suicide completion.

In EDs, C-SSRS screening is routinely administered by nurses during triage as standard of care, while in primary care clinics the C-SSRS screener will be self-administered by patients. The C-SSRS delivered as standard of care in either setting will be used as the basis for determining eligibility for completing a safety plan and eligibility for study enrollment. However, in ED settings, the C-SSRS will be re-

administered in a self-complete format for study participants as part of their baseline surveys, from which change in severity of suicidality will be measured when they self-complete the C-SSRS as part of 6 and 12-month outcome surveys.

The two C-SSRS scores collected during the baseline visit in EDs (nurse-administered vs. self-administered) will be compared as a sub-analysis to assess for any systematic differences in score. The results of this sub-analysis may inform future clinical practice as it relates to C-SSRS administration in SLHS EDs and other settings.

Table 3: C-SSRS Screening Tools by Timepoint, SPARC Trial

Timepoint	C-SSRS Assessment Used
Baseline Survey	Lifetime-Recent C-SSRS Screener (6 questions)

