9.3.4 Assessing Bias in Self-Reported Measures

In addition to self-reported uptake of care, for patients referred to a provider within SLHS, study staff will measure whether they attended one or more outpatient mental healthcare appointments or returned to care (ED utilization) for suicidality by looking at their electronic medical record in EPIC, reviewing an ED dashboard/EDIE System and by utilizing claims data when possible. However, we do not anticipate having complete data for patients who see a provider outside of SLHS. For these participants, study staff may review data in EPIC Care Link, or via other means to measure uptake of outpatient mental health treatment. Discrepancies are expected between data on uptake of treatment and care-seeking related to suicide from self-report compared to the data that can be directly measured. The analytic team will estimate the extent and direction of bias in a sub-set of participants from each comparator group who were referred to an SLHS provider by comparing self-reported uptake of outpatient mental healthcare services with what is recorded in EPIC. This will allow estimation of the degree of bias present in the self-reported data and determination of whether the extent of bias differs between the two comparator groups.

10. Description of Interventions

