12.3 Safety Outcomes

This protocol considers completed suicide, suicide attempts, and inpatient admission in the context of highly suicidal study participants as expected events. These will be routinely tracked as key safety outcomes. The following safety outcomes will be assessed for each participant at 6 and 12 months and reviewed by the Data and Safety Monitoring Board twice annually to determine whether the rate of safety outcomes differs by intervention arm:

- Death by suicide
- Attempted suicide
- Interrupted or aborted suicide attempt
- Psychiatric hospitalization
- Medical hospitalization related to self-harm or attempted suicide

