13.1 Data Collection

Baseline data are either already collected and recorded in EPIC as standard of care for all patients (demographic data, C-SSRS) or will be completed by the participant via REDCap survey immediately following enrollment and informed consent (Baseline Survey). Outcome data will be collected via REDCap survey or over the phone at 6 months and 12 months. *Table 4* includes a list of all study variables for the primary analysis, the tool to be used for data collection or source of the data, the frequency/timing with which they will be collected, whether they are routinely collected or will be collected specifically for the SPARC Trial, and which entity will collect them. Patient and provider satisfaction surveys will collect additional quantitative and qualitative data and will be collected via REDCap survey.

Table 4: SPARC Trial Variables of Interest and Other Data Elements

Variable	Tool/Source	Routinely collected as standard of care	Mode of contact	Who will collect
Outcomes (6 months)				
Suicidal ideation & behavior	C-SSRS	No	REDCap survey (text, email, or phone)	SLHS
Recent suicide attempts, suicide completion, & self-harm; lethal means	6- and 12-Months Suicide Attempts Survey, Vital Records, EPIC	No	REDCap survey (text, email, or phone)	SLHS
Loneliness	NIH Toolkit Loneliness Scale	No	REDCap survey (text, email, or phone)	SLHS
Uptake of outpatient mental health treatment	Self-report, EPIC, Claims data	Yes	REDCap survey (text, email, or phone)	SLHS

Return to ED for suicidality	Self-report, EPIC, EDIE, Claims data	Yes	REDCap survey (text, email, or phone)	SLHS
Outcomes (12 Months)				
Suicidal ideation & behavior	C-SSRS	No	REDCap survey (text, email, or phone)	SLHS
Recent suicide attempts, completion, & self-harm; lethal means	6- and 12-Months Suicide Attempts Survey; Vital Records, EPIC	No	REDCap survey (text, email, or phone)	SLHS
Loneliness	NIH Toolkit Loneliness Scale	No	REDCap survey (text, email, or phone)	SLHS
Uptake of outpatient mental health treatment	Self-report, EPIC, Claims data	Yes	REDCap survey (text, email, or phone)	SLHS
Return to ED for suicidality	Self-report, EPIC, Claims data, EDIE	Yes	REDCap survey (text, email, or phone)	SLHS

Exposures (Baseline)				
Age in years, age category (adult/peds)	EPIC	Yes	n/a	SLHS
Sex	EPIC	Yes	n/a	SLHS
Race and ethnicity	EPIC	Yes	n/a	SLHS
Address including Zip code of residence (urban/rural)	EPIC	Yes	n/a	SLHS
County of residence (urban/rural)	EPIC	Yes	n/a	SLHS

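### The health-record query for return to care names only the primary diagnosis and the reason code, so ED visits with suicidality coded only in another position can be missed

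*Protocol*

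**What the plan says.** Return to care for suicidality is a secondary outcome under Aim 1(c), with a stated hypothesis in favour of SP+CC. Section 9.3.3 gives it two main sources.

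- **Self-report.** "Return to care for suicidality will be assessed for study participants through self-report at 6 and 12 months".
- **Health-record query.** The query is to review "the number of times each patient returned to SLHS ED, the primary diagnosis, and the reason code (ICD-10"). The primary diagnosis is the only diagnosis position named.

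Other sources are listed with weaker commitment.

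- Section 9.3.3 adds that "study staff may also review available ED dashboards/EDIE System that includes health systems outside of SLHS", to pick up use of EDs elsewhere.
- Section 9.3.4 adds review of the EPIC record, together with "reviewing an ED dashboard/EDIE System and by utilizing claims data when possible". That sentence is worded for patients referred to a provider within St. Luke's.
- Table 4 in section 13.1 gives the sources for return to ED at 6 months as "Self-report, EPIC, EDIE, Claims data", and the same four at 12 months.

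Section 9.3.4 expects self-report and directly measured data to disagree, both on treatment uptake and on suicide-related care-seeking. The comparison it then describes is limited to "comparing self-reported uptake of outpatient mental healthcare services with what is recorded in EPIC".

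**The concern.** An ED visit after self-harm may carry an injury, a poisoning or an underlying psychiatric disorder as its primary diagnosis, with the suicidality or external-cause code lower in the list. If the reason code is also non-specific, the query as described does not identify the visit. A code list written later cannot repair this, because it can only search positions that were extracted.

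At stake is how completely Aim 1(c) is measured. Incomplete capture lowers the observed return rate and the power of the comparison. If capture differs between arms, the estimated effect is biased. The comparison that could show such a difference is not described for this outcome.

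**Working it through.** The protocol gives no return rate, target difference, power or coding sensitivity for this outcome, so there is no stated figure to reproduce. The calculation shows the mechanism only.

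**Inputs from the protocol.** Two-sided alpha 0.05 (section 14.1); 790 adults and 592 adolescents, with up to 30% dropout allowed for (section 14.2).

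**Assumptions.** 1:1 allocation, so 395 adults or 296 adolescents per arm; records available for everyone; true proportions of patients returning p1 = 20% and p2 = 12%; no false positives. Sensitivity s is the chance that a patient who truly returned is flagged.

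**Equal sensitivity.** Observed rates are s·p1 and s·p2.

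- Absolute difference: s·(p1 − p2).
- Risk ratio: (s·p2)/(s·p1) = p2/p1 = 0.60 for every s.
- Power: Φ[(d − 1.96·SE0)/SE1], where d is the observed difference and SE0 and SE1 are the pooled and unpooled standard errors.

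Adults, s = 1: d = 0.080, SE0 = √(2 × 0.16 × 0.84/395) = 0.0261, SE1 = √((0.20 × 0.80 + 0.12 × 0.88)/395) = 0.0259, power 0.867.

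Adults, s = 0.6: rates 0.120 and 0.072, d = 0.048, SE0 = √(2 × 0.096 × 0.904/395) = 0.0210, SE1 = √((0.120 × 0.880 + 0.072 × 0.928)/395) = 0.0209, power 0.630.

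| Sensitivity | Difference (points) | Risk ratio | Odds ratio | Power, adults | Power, adolescents |
|---|---|---|---|---|---|
| 1.0 | 8.0 | 0.60 | 0.545 | 87% | 76% |
| 0.8 | 6.4 | 0.60 | 0.558 | 77% | 65% |
| 0.6 | 4.8 | 0.60 | 0.569 | 63% | 51% |
| 0.5 | 4.0 | 0.60 | 0.574 | 55% | 43% |

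With assumed rates of 25% and 17%, adult power at the same four sensitivities is 79%, 67%, 53% and 45%. The pattern does not depend on one choice of rates.

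**Adding self-report.** Assume query sensitivity 0.6, self-report sensitivity 0.7, independent errors, and a return counted if either source shows it. Among survey responders the combined sensitivity is 1 − 0.4 × 0.3 = 0.88. If 70% respond, the overall figure is 0.7 × 0.88 + 0.3 × 0.6 = 0.80. Adult power is then about 77%, against 63% for the query alone and 87% for complete capture.

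**Visits versus patients.** If the query finds each visit with probability v, a patient with k visits is flagged with probability 1 − (1 − v)^k under independence. For v = 0.6 and k = 2 this is 1 − 0.16 = 0.84. Patient-level loss is therefore smaller than visit-level loss when patients return more than once.

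**Unequal sensitivity.**

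- 0.8 versus 0.6: 0.20 × 0.8 − 0.12 × 0.6 = 0.088. The difference is 8.8 points, larger than the true 8.0.
- 0.6 versus 0.8: 0.20 × 0.6 − 0.12 × 0.8 = 0.024, or 2.4 points.

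The direction of bias is not fixed.

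**The case against.** The strongest reply is that section 9.3.3 lists fields to review and does not state an exclusive case definition. Self-report stands beside the query, and Table 4 adds EDIE and claims. The reason code is a second field that may flag suicidality when the primary diagnosis is an injury. Suicide attempts and self-harm are also collected separately, by survey and from EPIC. Code lists and rules for combining sources are commonly left to the SAP, which is not shown.

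Much of this stands. A reader might infer that the whole outcome rests on the primary diagnosis; the protocol does not say so. Nor is a missing code list or combination rule the point here. What remains is that the fields to be extracted are stated in the protocol, and stated narrowly. The other sources are only a partial safety net: self-report is absent for patients who do not complete the survey, EDIE review is discretionary, and claims are used when available.

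Two supporting passages are easily over-read. Section 12.3 lists "Medical hospitalization related to self-harm or attempted suicide" as a safety outcome, but says nothing about how such episodes are coded. Section 9.2 states that "In EDs, C-SSRS screening is routinely administered by nurses during triage as standard of care". That describes routine practice and does not establish a recorded score at every visit; Table 4 tracks screening rates as a process variable.

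**Conclusion.** The point holds for the record component of this secondary outcome. As described, the query can miss St. Luke's ED visits where suicidality or self-harm is coded only in a secondary or external-cause position, and the other sources recover some of them but not reliably all. The planned quantitative comparison with EPIC does not cover return to care.

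The size cannot be stated, because it depends on the return rate and on coding practice, and the protocol gives neither. The power figures above are illustrations on assumed rates and sensitivities.

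Two stronger conclusions are tempting. One is that the arm difference must shrink. That is true of the absolute difference when sensitivity is equal between arms and specificity is high; the risk ratio is then unchanged, the odds ratio moves little, and the main cost is power. With unequal sensitivity the bias can run either way. The other is that the loss falls mainly on visits after actual self-harm. That is plausible from how injuries are coded, but nothing in the protocol shows it.

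**What to change.** 1. In section 9.3.3, extract all diagnosis positions for each ED visit, including external-cause codes, together with the reason code.
2. Count an ED visit as a return for suicidality if a code from one list, fixed before unmasking, appears in any position or in the reason code.
3. Keep the count based on primary diagnosis and reason code as a sensitivity analysis.
4. Extend the self-report versus EPIC comparison in section 9.3.4 to return to care, by arm, so that unequal ascertainment can be seen.
5. Optionally, where a triage C-SSRS is recorded for the visit, use it to check the code list. It should not define the outcome, because a positive screen can occur at an unrelated visit.

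The cost is a few more fields in an EPIC extraction that is already planned with specialist support, and one more comparison of data already being collected. The downside is some loss of specificity: visits where suicidality was incidental will be counted. The retained narrow count shows how much that matters.

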9.3.4 Assessing Bias in Self-Reported Measures

In addition to self-reported uptake of care, for patients referred to a provider within SLHS, study staff will measure whether they attended one or more outpatient mental healthcare appointments or returned to care (ED utilization) for suicidality by looking at their electronic medical record in EPIC, reviewing an ED dashboard/EDIE System and by utilizing claims data when possible. However, we do not anticipate having complete data for patients who see a provider outside of SLHS. For these participants, study staff may review data in EPIC Care Link, or via other means to measure uptake of outpatient mental health treatment. Discrepancies are expected between data on uptake of treatment and care-seeking related to suicide from self-report compared to the data that can be directly measured. The analytic team will estimate the extent and direction of bias in a sub-set of participants from each comparator group who were referred to an SLHS provider by comparing self-reported uptake of outpatient mental healthcare services with what is recorded in EPIC. This will allow estimation of the degree of bias present in the self-reported data and determination of whether the extent of bias differs between the two comparator groups.

10. Description of Interventions

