9.3.2 Uptake of Outpatient Mental Health Services

Uptake of outpatient mental health services will be measured at 6 and 12 months in two ways: through self-report, and (wherever possible) directly via electronic health records or using internal claims data.

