10.2 Safety Planning Intervention Plus Phone-Based Follow-Up (SPI+)

The Safety Planning Intervention (SPI+)¹⁻⁷ includes safety planning plus a structured telephone-based intervention following discharge from the emergency department or departure from a primary care clinic. For the SPARC Trial, Hotline follow-up specialists will call participants within 72 hours of study enrollment to (1) conduct a brief suicide risk assessment; (2) review and revise the participant’s connection and support plan or safety plan; and (3) provide support with treatment engagement, if indicated. Participants will receive at least one and optional additional phone calls as part of the SPI+ follow-up intervention generally delivered according to the following schedule: days 3, 7, 14, 30, 60, 90.^{8,9} Modifications may be made to the schedule due to weekends, holidays, or participant availability, and additional calls may be scheduled as desired by the participant. The follow-up will stop once the participant is successfully engaged in outpatient treatment or does not desire further follow-up support. In instances where participants cannot be reached for an initial phone call within 72 hours, Hotline staff will continue to attempt to schedule and complete the phone call. A minimum of three attempts to schedule and complete each phone call will be made.

This version of the intervention differs from the Stanley/Brown SPI+ model in that the structured follow-up

will be conducted by Hotline follow-up specialists, rather than by specially trained social workers or psychologists. In this pragmatic clinical trial, we are committed to testing a model that could be feasibly scaled up and replicated in other rural and resource-limited settings. The schedule was adopted from similar military follow-up programs: the Marine Intercept Program⁹ and the Navy Sailor Assistance and Intercept for Life (SAIL) Program.⁸ We selected this schedule given that we wanted to offer a longer follow-up window than the traditional SPI+ in order to support treatment engagement because connecting with outpatient behavioral health treatment (such as a counselor or therapist) typically takes 4-6 weeks for patients at low risk for suicide in our health system.

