10.4 Safety Planning Intervention + (SP+CC)

SP+CC will include safety planning, plus caring contacts from the Hotline. Suicide prevention hotlines have been shown to be an effective means of mitigating active suicide risk.^{58,59} **SP+CC follow-up will consist of one phone conversation, whenever possible within the first 72 hours following study enrollment,** to connect and establish rapport between the follow-up specialist and participant. In instances where participants cannot be reached within 72 hours, Hotline staff will make at least three attempts. If the phone call cannot be successfully completed after at least three attempts, the caring contacts will be started without the phone call.

The call will be followed by a series of 25 personalized caring contacts sent over the course of 12 months via text message or email.⁶⁰ The frequency and cadence of caring text or email messages will be consistent for all participants according to a schedule that was developed in consultation with PLES Advisors to ensure it is culturally and age appropriate. Caring text or email messages will be sent according to the following schedule: three in the first week, 6 weekly, 6 bi-weekly, 4 monthly; two bi-monthly, and one each for the participant's birthday, Thanksgiving, Christmas, and New Year's (total of 25 over 12 months).⁶⁰ The exact schedule and content of the messages may vary slightly to account for weekends and holidays (messages will generally be sent M-F during working hours). While there is no expectation that participants respond to the text messages, some participants may choose to respond. Hotline Follow-Up Specialists will review incoming text messages and phone calls from study participants and will respond according to the Hotline's internal operating procedures. These additional contacts will take place outside of the structured study protocol and will not be under the purview of SLHS institutional policies. The number of individual responses, content, and timing of text or email messages will be tracked and shared with the study team. Response and ongoing contacts as part of the Hotline's processes will not alter the timing or frequency of caring contacts established by the study protocol.

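### The self-report bias check in section 9.3.4 compares any outpatient care with EPIC alone, so even among SLHS-referred participants it cannot tell over-reporting from visits made outside SLHS

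*Protocol*

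**What the plan says.** Section 9.3.2 measures uptake of outpatient mental health services "through self-report, and (wherever possible) directly via electronic health records or using internal claims data". Neither that section nor 9.3.4 limits the outcome to visits at SLHS.

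Section 9.3.4 then deals with error in self-report. On directly measured data it concedes that "we do not anticipate having complete data for patients who see a provider outside of SLHS". For outside care it adds that "study staff may review data in EPIC Care Link, or via other means to measure uptake of outpatient mental health treatment", which is optional. Claims data are mentioned for SLHS-referred patients, but only when possible.

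The bias estimate is made "in a sub-set of participants from each comparator group who were referred to an SLHS provider". The method named for this subset is "comparing self-reported uptake of outpatient mental healthcare services with what is recorded in EPIC". EPIC is the only reference named in that sentence. The section expects the result to show the degree of bias in self-report and to allow "determination of whether the extent of bias differs between the two comparator groups".

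**The concern.** The two sides of the comparison do not cover the same thing. The self-reported item is outpatient mental health care anywhere; the reference is what one health system's record contains. EPIC can confirm that a visit took place, but it cannot show that none took place elsewhere.

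Restricting the subset to SLHS referrals narrows the gap without closing it, because membership depends on where a participant was sent and not on where care was received. Someone referred within SLHS who sees an outside therapist and says so truthfully has a yes on self-report and nothing in EPIC. In this comparison that looks the same as an over-report.

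What is at stake is the conclusion that 9.3.4 wants to draw. If unrecorded outside visits and false reports fall in the same cell, neither the size nor the sign of the bias is identified. A difference between arms in apparent bias could reflect a difference in uptake or in outside use. Section 10.2 says the SPI+ calls will "provide support with treatment engagement, if indicated", whereas in section 10.4 the single SP+CC call is "to connect and establish rapport between the follow-up specialist and participant". A difference in care-seeking by arm is therefore possible, although the protocol does not say in which direction outside-only care would move.

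**Working it through.** The protocol states no figure for this check, so there is nothing to reproduce. The argument is a misclassification identity, followed by an illustration with assumed values.

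**Notation, within the SLHS-referred subset of one arm**
- p: true share with any outpatient mental health care (not given; assumed 0.5 to 0.6).
- q: share of those attenders seen only outside SLHS (not given; assumed 0 to 0.3).
- se, sp: sensitivity and specificity of self-report.
- EPIC is assumed to record every SLHS visit and no outside visit.

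**Identity**
- P(self-report yes) = p·se + (1 − p)(1 − sp)
- P(EPIC yes) = p(1 − q)
- True net bias = P(self-report yes) − p
- Apparent net bias = P(self-report yes) − p(1 − q)
- Apparent minus true = p·q, the share of the subset with outside-only care.

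**1. Accurate self-report (se = sp = 1), p = 0.5.** True bias is 0 throughout.

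| q | apparent over-reporting, p·q |
|---|---|
| 0 | 0 |
| 0.05 | 2.5 points |
| 0.10 | 5 points |
| 0.20 | 10 points |
| 0.30 | 15 points |

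**2. Difference between arms, self-report still accurate in both**
- Equal p and q in both arms: difference 0.
- p = 0.5 in both, q = 0.20 against 0.10: 0.10 − 0.05 = 5 points, all false. If the two q values change arms, the sign reverses.
- q = 0.20 in both, p = 0.6 against 0.5: 0.12 − 0.10 = 2 points, all false. Higher uptake alone is enough when q is above 0.

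**3. Sign of the bias, with real under-reporting (se = 0.9, sp = 1, p = 0.5).** P(self-report yes) = 0.45, so true bias is 0.45 − 0.50 = −5 points.
- q = 0: apparent bias 0.45 − 0.50 = −5 points, which is correct.
- q = 0.10: 0.45 − 0.45 = 0, so the under-reporting is hidden.
- q = 0.20: 0.45 − 0.40 = +5 points, so the sign is reversed.

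**4. What the data can identify.** Among participants with a recorded SLHS visit, the share answering no is p(1 − q)(1 − se) / [p(1 − q)] = 1 − se. In case 3 this is 10% whatever q is, provided SLHS and outside attenders report equally well. The cell with self-report yes and no EPIC visit holds p·q·se + (1 − p)(1 − sp). It mixes truthful outside care with false reports, and EPIC alone cannot split it.

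**The case against.** The strongest reply is that the protocol saw this problem. It states the gap in outside data and limits the check to people referred to SLHS, for whom EPIC should be most complete. If nearly all attenders in that subset used SLHS, q is close to 0 and the error disappears. This stands: the defect is residual and its size is unknown.

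A second reply is that combining sources in a cross-tabulation is ordinary SAP detail. That would hold if the protocol had left the comparison open. It names the comparison and the inference to be drawn from it, so the wording of 9.3.4 is fair to question. The protocol does not say in terms that a yes without an EPIC visit is an over-report, but reading the comparison as self-report bias amounts to that.

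A reader might go further and infer that a real SPI+ gain would be relabelled as over-reporting and adjusted away, in favour of the hypothesis that SP+CC raises uptake. The documents do not support this:
- The protocol nowhere says the secondary outcome will be corrected or discounted from this check.
- The direction is open. Engagement support could lead SPI+ participants to outside providers, or to the SLHS appointment they were referred for, which would lower the outside-only share.
- The row in Table 2 on counselling about barriers to care refers to Hotline calls in general, and SP+CC also includes one such call. Only the engagement support in 10.2 is stated for SPI+ alone.
- The four to six weeks in 10.2 explains the call schedule and says nothing about patients going outside SLHS.

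**Conclusion.** The point holds in limited form. As written, the check in 9.3.4 cannot separate over-reporting from unrecorded outside visits. It overstates net over-reporting, or understates net under-reporting, by p·q. The protocol gives neither p nor q. Over the assumed range with p = 0.5 and q from 0 to 0.3, the error runs from 0 to 15 points, and it is exactly 0 if all attenders in the subset used SLHS. A between-arm difference in bias would be false to the extent that p·q differs by arm. The documents give no evidence that it does and no basis for a direction.

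This concerns a validation sub-analysis of one secondary outcome. It does not affect the primary outcome or the sample size. It is worth changing because the change is cheap and the present wording promises more than the comparison can show.

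**What to change.** Reword the bias check in 9.3.4 so that each source is used only for what it can show.

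- **Under-reporting, by arm:** the proportion answering no among participants with a visit recorded in EPIC, claims or EPIC Care Link.
- **Over-reporting, by arm:** count a self-reported yes with no EPIC visit as over-reporting only where claims data for the period are complete and also show no visit. Report the remaining such cases by arm as unverifiable disagreement, not as bias.

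The sources are already listed in 9.3.2 and 9.3.4, so the work is wording and a cross-tabulation. Because 9.3.2 speaks of internal claims, the team should confirm that the claims cover outside providers before treating them as complete. The cost is that over-reporting is estimated in a smaller group with a wider interval. How the sources are combined to define the uptake endpoint itself is a separate choice and need not change for this point.
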